9.8 QUALITY CONTROL

The EMR information [REDACTED] receives is loaded into the input database unchanged. The incoming data are subject to quality control steps to ensure all the expected data are received and files are complete and readable. Changes in historic data are labeled as such and both original and modified values retained.

Input data are transformed into the operational database through a quality assurance process to ensure the validity of each data point. Metrics are tracked longitudinally to ensure logical consistency visits over visit, and are required to fall within specified limits (thresholds have been set using clinical insight from active retina specialists). Incidental Personal Health Information (PHI) contained in text fields are removed, information in text strings that contain multiple data elements are broken down into separate analyzable and standardized cells. [REDACTED]
[REDACTED]

All data shared with BI will be at an aggregated stage, and will be fully de-identified and HIPAA compliant

9.9 LIMITATIONS OF THE RESEARCH METHODS

As with real world data entered during patient encounters, there are limitations due to the entry process and general operations of both physicians and clinics. The [REDACTED] database includes only data from visits that occurred at the practices contributing to the database. Anything occurring during visits to a retina specialist/ophthalmologist in a different practice, state, country etc. is not captured.

[REDACTED] does receive information on previous history, referrals, etc. from overall patient history fields in attempt to gain insights on potential previous physicians, however [REDACTED] completely relies upon the physician to enter these data. This is a limitation of the study regarding the incidence and prevalence of the study diseases.

Retinal specialists are the primary specialty that will observe and treat all forms of AMD. However, there is a portion of mild dry AMD patients who are being observed by their general ophthalmologist. As this study will focus on GA specifically, there should not be a concern with underrepresentation in the database, as it is the most severe form of dry AMD. Out of the 1.6 million eyes with 1+ visit to in the [REDACTED] in 2022, dry AMD was the most prominent disease with ~180,000 eyes, twice as large as those with wAMD. While this study will identify newly diagnosed cases of GA and wAMD, there is a possibility that a patient was diagnosed prior by an ophthalmologist or other retina specialist. As these are severe versions of AMD that are handled only by retina specialists in the USA, it is a limitation that must be addressed.

Prevalent cases are less affected as per the study definitions they are being seen over a multiple year span in the same dataset. While it is possible, they are seeing other healthcare

BOEHRINGER INGELHEIM Group of Companies**NIS Protocol Template****Study number: 1484.0014****Page 27 of 30****Document number: <insert>**

professionals during this time frame, they are continuing to visit their retina specialist for follow up. Patients who leave the panel for any number of reasons (death, moving, poor experience) are only able to be identified as lost to follow up. No other claim can be made on these cases, and for the study purposes they would no longer be included in any analysis from that point onwards.

For portions of the analysis where visual acuity (or other key clinical outcomes) is the primary outcome, patients are only included in the analysis when a visual acuity reading was available. In this way, it is possible that a bias is occurring in patients who are willing to have their vision recorded at every visit, or who are visiting their doctor on a more regular basis.

██████████ can only analyze visits where VA is taken, any visual acuity gains or losses that occur between visits cannot be captured. The last VA taken, or other clinical measures, is not automatically carried forward between visits, or in other words, last observation carried forward or other automatically carried forward outcomes are not utilized as ██████████ standards. These methods are available for exploration, but also carry their own limitations.

Regarding the progression analysis over a 5-year period, one limitation using this database is the length of patient follow-up time. While running feasibility, the ██████████ database showed a mean of 1.9 years of follow up. This however also includes patient who were diagnosed in 2022 for example and do not have the opportunity for 3 years of follow up. One way to address this limitation is to restrict those analysis to those patients with at least two entries with available data on progression during the follow up, however this may have the caveat to reduce the cohort of patients available for analysis. This will be explored during data readouts. Alternative methods of analysis such as Kaplan Meier may be a useful alternative to mitigate bias when analyzing rates over time.

As an overall limitation of the dataset, Data in the EHR is recorded by the physician or scribe under the direction of the physician. Physicians do not tend to enter data that is not directly relevant to the patient's current condition and tend not to enter null information. There is no real time validation of the information entered during the encounter either in terms of completeness or accuracy. However, ██████████ works extensively with the physicians providing analysis of their own data. As such, this is a crucial step in the data validation process, as physicians analyzing their own data over the years has provided insights on better coding, data entry and completeness. This limitation will affect the covariates related to comorbidities outside of retina. The current workaround is to use the systemic medications list provided to identify the treatment of these comorbidities (diabetes, hypertension etc.). However, this field also comes with its own limitation of relying on the physician/patient to provide an accurate summary of each patient's medication list.

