- Follow up reading at Month 24, 36, 60: +/- 60 days

Incidence (new cases) and prevalence of GA will be captured, based on the ICD 10 diagnosis codes. On a calendar basis, all newly diagnosed patients will be identified and count as incident patients. Patients with a previous diagnosis of GA in the past years (with respect to a given calendar year), will be counted as prevalent cases during that calendar year.

The yearly counts of newly diagnosed or prevalent cases, will help to understand the progression of the overall disease.

BOEHRINGER INGELHEIM Group of Companies**NIS Protocol Template****Study number: 1484.0014****Page 18 of 30****Document number: <insert>****9.3.2.2 Secondary outcomes****• Retinal Disease Related HCRU Outcomes**

Change in physician care over time will be evaluated from the incident date of GA, and assessed on a yearly basis in order to assess if physician habits have changed over time, particularly following September 2021 and additionally following [REDACTED].

Patient visits: A patient visit (or encounter) is identified in the database any time a patient visits one of the panel physicians. Since the [REDACTED] database consists only of private practicing retina specialists, these are the only types of visits analyzed in the study.

If a patient visits the physician at a hospital, institution, or has an emergency room admission, the event will not be captured. For all patient visits, it is assumed that both eyes are being seen/assessed even in the primary visit reason is for one particular eye. In this sense, all visits will contribute to both eyes and any outcomes at these visits will be available for assessment.

Treatments: The documentation includes **all treatments** including injections, laser treatments, and other procedures. The type of diagnostic procedure done, and the results of these diagnostics are also recorded for most encounters. For any visit, it is assumed that both eyes are being seen, even if only one eye receives any treatment.

Other medical procedures: for example, cataracts removal, eye lid (ptosis correction), etc.

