An additional analysis will be made to extrapolate the prevalent results to a national – US-level. For that analysis, the prevalence of GA will be considering all patients seen by a retina specialist in the given year. With this metric, estimation on a national level will be done using an estimation of all practicing US retina specialists.

When analyzing the rate of progression from dry AMD to GA, a conversion analysis will be done. This will include the overall rate of dry AMD eyes developing GA, along with a Kaplan Meier analysis assessing the rate of conversion over time. This analysis will track progression by month from diagnosis, censor any patient at the final visit in the database, and identify the incident GA diagnosis as an event.

Analysis for objectives:

To evaluate patients' management (i.e. patients visits and procedures) over the study period.

BOEHRINGER INGELHEIM Group of Companies**NIS Protocol Template****Page 24 of 30****Study number: 1484.0014****Document number: <insert>****Patients' management**

All visits, treatment, checkups, procedures, and other will be summarized across the duration of the study time frame as well as between the index diagnosis and at the 12 (24, 36, 48, 60) month follow up period.

An additional sub analysis will be conducted to evaluate the changes in the frequency of patients visits or procedures, checkups, after the third quarter of 2021 and after [REDACTED].

Summary will include descriptive statistics; continuous variables will be described by absolute numbers, the mean (SD), median and range, while categorical variables will be described using frequency and proportion. Absolute numbers (n), and correspondent percentage (%) of the variables (either eyes or patients as appropriate) will be always included in the description of the results.

Analysis for objective:

To describe and compare patients' characteristics in different progression subgroups (i.e. those that develop eCNV/those that not), of the overall GA population.

The following groups will be evaluated to better understand progression:

1. Patients that [REDACTED]

vs. those that do not in the 1, 2, 3, 4 and 5 years of follow up period.

2. Patients that [REDACTED]

vs. those that do not in the 1, 2, 3, 4 and 5 years of follow up period.

3. Patients with subfoveal lesion location vs. those with extrafoveal lesion location.

For this subgroup of patient's characteristics will be described and compared.

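### Counts of cataract removal and ptosis correction cover only operations done at the contributing retina practices, so as a measure of GA patients' procedure use they are too low by an unknown amount

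*Combined protocol and SAP*

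**What the plan says.** Section 8 makes patient management, meaning visits and procedures, a secondary objective. Section 9.3.2.2 sets out the matching outcome under the heading "Retinal Disease Related HCRU Outcomes" and includes this line: "Other medical procedures: for example, cataracts removal, eye lid (ptosis correction), etc". Its Treatments paragraph describes the documentation as covering every treatment, with injections, laser and other procedures among them.

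The same section restricts the source. The "database consists only of private practicing retina specialists, these are the only types of visits analyzed in the study". It adds: "If a patient visits the physician at a hospital, institution, or has an emergency room admission, the event will not be captured". Section 9.4 describes the record as continuous only while the patient stays in the same practice, and complete for what that practice delivered. Section 9.9 adds that care in another practice is lost: "Anything occurring during visits to a retina specialist/ophthalmologist in a different practice, state, country etc. is not captured".

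For the analysis, section 9.7.1 (Patients' management) says: "All visits, treatment, checkups, procedures, and other will be summarized across the duration of the study time frame". The same summaries are repeated from index to 12, 24, 36, 48 and 60 months, with a sub-analysis of changes after the third quarter of 2021. No capture correction or in-practice label is stated.

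**The concern.** The two named operations are on the lens and the eyelid. They sit in an outcome headed as related to retinal disease, and the data come from retina practices alone. If a GA patient has either operation at a hospital, at an institution or in another practice, it does not enter the database as a procedure. A patient with no record may have had no operation, or may have had it elsewhere, and the planned summaries do not separate the two.

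What is at stake is how one part of the patient-management objective is read. Without a label, a table of cataract removals at 12 to 60 months can be taken as the rate at which GA patients have that surgery, when it is the rate at which contributing practices recorded doing it. Section 9.3.2.2 encourages the wider reading by calling the treatment documentation all-inclusive, without the within-practice qualifier that section 9.4 attaches.

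**Working it through.** The plan states no procedure rate or capture fraction, so there is no figure of its own to reproduce. The check has three parts.

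**1. The passages side by side**

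| Point | Where | Content |
|---|---|---|
| What is counted | 9.3.2.2 | Other procedures, with lens and eyelid surgery as examples |
| What is captured | 9.3.2.2, 9.4, 9.9 | Care at contributing private retina practices only |
| Claimed completeness | 9.3.2.2 | All treatments, no qualifier |
| Claimed completeness | 9.4 | All treatments delivered through the practice |
| Consequence drawn from outside care | 9.9 | Incidence and prevalence of the study diseases |
| Consequence drawn for procedure counts | none | Not mentioned |

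Missing outside care removes events and cannot add any, so the direction of the error follows from the documents alone.

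**2. Size, as a sensitivity range**

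Let c be the share of these operations among panel patients that is recorded as a procedure in the database. Then

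observed proportion = c × true proportion, and relative undercount = 1 − c.

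The relative undercount does not depend on the true proportion. To show the scale, take the 72,718 GA patients in section 9.5 and assume that 10% truly have such a procedure: 0.10 × 72,718 = 7,272. Both the 10% and the values of c are assumptions.

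| Assumed c | Patients observed | Observed % | Undercount |
|---|---|---|---|
| 0.05 | 364 | 0.5 | 95% |
| 0.25 | 1,818 | 2.5 | 75% |
| 0.50 | 3,636 | 5.0 | 50% |
| 0.75 | 5,454 | 7.5 | 25% |
| 0.95 | 6,908 | 9.5 | 5% |

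The range runs from trivial to nearly total, and nothing in the documents narrows it.

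**3. Whether the plan holds a less biased source**

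Section 9.3.3.2 already derives cataract, phakic and pseudophakic status from codes and free text. An eye recorded as phakic or cataractous and later as pseudophakic has had its lens replaced in between, wherever that was done. Lens status can therefore reveal surgery that the procedure record misses. Nothing comparable is planned for the eyelid.

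The pseudophakic definition has a fault that must be mended first: it lists H35.31 among its codes. In Table 1 every ICD-10 code for dry AMD and for GA begins with H35.31. The text speaks of a combination of codes and free text without saying how they combine. If any one code suffices, and H35.31 is read as a stem, every eye with a GA code is classed as pseudophakic by its GA diagnosis, and the change in lens status would mark the AMD diagnosis and not surgery.

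**The case against.** The strongest reply is that the plan never claims to measure surgery done anywhere. Section 9.3.2.2 gives the purpose of this outcome as seeing whether physicians' habits changed, and says of retina-specialist visits that "these are the only types of visits analyzed in the study". For that purpose in-practice counts are the right quantity, and the non-capture of hospital care is disclosed next to the outcome. The operations appear in one line of examples in a descriptive secondary outcome; visits, injections and laser are not in question, and no primary objective is touched.

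Much of this stands. The counts are valid as procedures delivered at the contributing practices, and the plan nowhere says that an absent record means no operation. It does not settle the matter, because section 8 frames the objective around patients' management, section 9.7.1 carries no in-practice label, and the Treatments paragraph reads as complete. Disclosure in general terms has not reached this outcome.

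The reply is also right that lens status is imperfect. Section 9.3.3.2 concedes that phakic eyes have no explicit code, and section 9.9 says that physicians tend not to enter information that is not relevant to the current condition. A change in recorded status may partly reflect when someone wrote it down.

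**Conclusion.** The point holds for direction, not for size. As a measure of GA patients' use, the counts of cataract removal and ptosis correction are too low by an unknown, possibly large amount, as long as any of these operations take place outside the contributing practices. As in-practice counts they are sound but unlabelled.

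Three stronger readings are tempting, and the documents do not support them:

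- **That the counts will be several-fold too low.** This needs the share of these operations done outside the panel. The documents do not say who performs them or where, so any multiple would only restate an assumed c.
- **That the panel's estimated 15–20% share of US retina specialists (section 9.2.1) shows how much is captured.** That figure is a share of physicians nationally, not the share of panel patients' operations recorded in the database.
- **That the comparison around the third quarter of 2021 must be biased too.** With true rates r1 before and r2 after, and a stable c, the observed ratio is (c × r2)/(c × r1) = r2/r1, so c cancels. Bias in the ratio would need capture to change over time, which nothing in the documents shows. An absolute difference would still shrink, to c × (r2 − r1).

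**What to change.** 1. In section 9.3.2.2 and section 9.7.1 (Patients' management), define the procedure outcome as procedures delivered at the contributing practices, and label it so in every table. Add the same qualifier to the Treatments paragraph.
2. In section 9.9, extend the outside-care limitation to the procedure counts.
3. Report ptosis correction only under that label, or drop it.
4. Report cataract removal per eye as the first pseudophakic record after a phakic or cataract record, dated to the interval between those two visits. The denominator is eyes with a phakic or cataract record, since an eye first seen as pseudophakic cannot contribute a change.
5. Before step 4, remove H35.31 from the pseudophakic definition in section 9.3.3.2 and state how its codes and free text combine.

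The cost is protocol wording, one corrected definition and one derived variable from lens data that the plan already intends to extract. The downsides are real. Surgery is dated only to an interval, and lens status depends on free text and on when it was documented. Surgery elsewhere is seen only if the eye returns and its lens status is recorded, so some undercount remains. Ptosis correction is no longer available as a measure of total use.

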9.10 OTHER ASPECTS**9.10.1 Data quality assurance**

As this data is retrospective and de-identified in nature, there is no opportunity for patient influence and is therefore exempt from IRB review.

A quality assurance audit/inspection of this study may be conducted by the sponsor. The quality assurance auditor will have access to the database.

BOEHRINGER INGELHEIM Group of Companies**NIS Protocol Template****Study number: 1484.0014****Page 28 of 30****Document number: <insert>****9.10.2 Study records**

This is a study based on existing data, [REDACTED] is an existing database that contained the electronical medical records of patients as described in the data source section.

The investigator/institution will permit study-related monitoring, audits, IRB/IEC review and regulatory inspection, providing direct access to all related source data/documents.

CRFs/eCRFs and all source documents, including progress notes and copies of laboratory and medical test results must be available at all times for review by the sponsor's clinical study monitor, auditor and inspection by health authorities (e.g. US Food and Drug Administration (FDA)).

9.10.3 Completion of study

This is a study based on existing data, and there is no EC competent for the use of the [REDACTED] database.

10. PROTECTION OF HUMAN SUBJECTS

This is a study based on existing data and the data analysis will be conducted using anonymized patient level information. The use of the [REDACTED] database do not require any submission or approval from an Institutional Review Board (IRB).

10.1 STUDY APPROVAL, PATIENT INFORMATION, AND INFORMED CONSENT

The conduct of the study using the [REDACTED] database does not required of any Institutional Review Board/Independent Ethics Committee approval. No additional Competent Authority should be consulted to the initiation of this NIS. As this study is based on existing data, patients consent is not necessary to be obtained.

10.2 STATEMENT OF CONFIDENTIALITY

Individual patient medical information obtained as a result of this study is considered confidential and disclosure to third parties is prohibited with the exceptions noted below. Patient confidentiality will be ensured by using patient identification code numbers.

Treatment data may be given to the patient's personal physician or to other appropriate medical personnel responsible for the patient's welfare. Data generated as a result of the study need to be available for inspection on request by the participating physicians, the sponsor's representatives, by the IRB/IEC and the regulatory authorities (when applicable).

11. ADVERSE EVENT AND SERIOUS ADVERSE EVENT COLLECTION AND REPORTING

Not applicable based on secondary use of data without any potential that any employee of BI or agent working on behalf of BI will access individually identifiable patient data.

BOEHRINGER INGELHEIM Group of Companies**NIS Protocol Template****Page 29 of 30****Study number: 1484.0014****Document number: <insert>****12. REPORTING TO HEALTH AUTHORITIES**

Adverse event reporting to regulatory agencies are done by the Marketing Authorization Holder (MAH) according to local and international regulatory requirements.

13. PLANS FOR DISSEMINATING AND COMMUNICATING STUDY RESULTS

The rights of the investigators, and of the sponsor with regard to publication of the results of this study are described in the “terms of collaboration” document. As a general rule, no study results should be published prior to finalization of the Study Report.

15. ANNEX 1. ADDITIONAL INFORMATION

All definitions of variables outlined during the protocol are summarized in an excel file to keep this document concise and for ease of reference. The file has been sent along with the protocol and a link can be found here:

[CODES APPENDIX.XLSX](#)

BOEHRINGER INGELHEIM Group of Companies

NIS Protocol Template

Page 30 of 30

Study number: 1484.0014

Document number: <insert>

